8.1 Baseline Laboratory Tests

The required baseline laboratory tests at different levels of MMC are shown in Table 2. Islet autoantibodies mainly involve insulin cell antibody (ICA), insulin autoantibody (IAA) and glutamic acid decarboxylase antibody (GAD-Ab), and it is proposed to detect GAD-Ab at least to help classify the type of diabetes. All laboratory tests will be performed in local sites.

8.1.1 HbA1c Measurements

Local HbA1c for regional and county MMCs should be measured by 18/35 high-performance liquid chromatography (HPLC).

8.1.2 Glucose Tolerance Test

For the glucose tolerance test, participants will be required to fast overnight to undergo a standard steamed bread meal test. First, at fasting, blood is drawn for measuring fasting blood glucose (FBG), fasting serum C peptide and/or insulin, liver and kidney function, blood lipid profiles and other laboratory tests. For postprandial measurements, 100 g steamed bun will be given. After the first bite, the patients will have blood drawn 2 hours later in order to measure postprandial blood glucose (PBG), postprandial serum C peptide and insulin. Under certain circumstances, 3h oral glucose tolerance test (OGTT) in five time points will be undertaken. Participants are forbidden to smoke, drink or eat anything throughout the glucose tolerance test. Patients who have been diagnosed with diabetes take their hypoglycemic and other agents normally during the test.

8.2 Baseline Examination of Diabetes-related Complications

8.2.1 Fundus Photography

Fundus examination is performed for all diabetic patients by an experienced and trained technician. One color macula-centered fundus image will be acquired from each eye. Fundus images are taken without pupil dilation and with a 45-degree field of view. The worse diabetic retinopathy (DR) classification of the two eyes will be chosen as the final patient-level DR grade. The status of DR is defined as "yes" if mild non-proliferative DR (NPDR) or above is present. We describe DR grade by

following definitions: referable DR (moderate NPDR or above); vision-threatening DR (VTDR, severe NPDR or above and/or clinically significant macular edema [CSME])[12]. The definition for VTDR may be modulated and specified in certain studies.

8.2.2 Screening for Diabetic Neuropathy

To assess diabetic peripheral neuropathy (DPN), electromyography is prioritized in hospitals where conditions are available. The instrument (NC-stat® DPN CheckTM) can also be used to measure the amplitude and conduction velocity (CV) of the sural nerve in legs of the patient. The amplitude has been found to decrease by about 1 μ V per decade with age. Sural nerve conduction velocity is correlated with age and height, decreasing by 1.3 m/s per 10 years and 2.0 m/s per 10 cm height. After entering age and height, the device will automatically determine the status of DPN (normal, mild, moderate or severe) according to the levels of amplitude and CV with reference to the calculated normal limit.

8.2.3 Measurements of brachial-ankle pulse wave velocity (baPWV) and ankle-brachial index (ABI)

The noninvasive measurements of baPWV and ABI will be performed using an automated recording apparatus (BP-203RPE III, form PWV/ABI or HBP-8000, Omron Healthcare Co.) in the supine position after resting for at least 5 minutes[17]. Suitable cuffs will be attached to participants around both arms and ankles to take measurements of both the brachial and tibial arteries by a trained operator. BaPWV values will be calculated as dividing the transit distance (the distance from the heart to

the ankle minus the distance from the heart to the arm) by the transmission time, which equals to the time interval from the initial increase in the brachial to that of tibial artery waveforms[18]. The mean or greater value of the right and left baPWV will be analyzed. Generally, the upper quartile of baPWV is defined as arterial stiffness. The systolic blood pressure (SBP) at the ankle is divided by the SBP at the upper arm to calculate the indicator ABI, which is used to screen peripheral arterial disease.

8.2.4 Carotid Ultrasonography

Carotid intima-media thickness (IMT) as well as plaques is examined using a Doppler apparatus. The location to measure IMT of the common carotid artery (C-IMT) is the distal wall of the common carotid artery, 10 mm proximal to the bifurcation[19]. An average or larger value of C-IMT on the left and right sides will be recorded for analysis. Carotid plaque will be determined as "yes" if the plaque is present in either side of the carotid and its branches.

8.2.5 Electrocardiogram (ECG) and Echocardiogram

The patients will undergo ECG and echocardiographic examinations to detect cardiac abnormalities. Structured report will be recorded for analysis. In the ECG report, the cardiac rhythm and diagnosis will be required to record. In the echocardiographic report, besides the final diagnosis information, the following parameters will also be obtained: left atrial diameter (LAD), interventricular septal thickness, left ventricular internal diameter in systole and diastole, posterior wall thickness of left ventricle, left ventricular ejection fraction (LVEF), and inner diameter of aortic root.

8.3 Clinical Examination at Follow-up Visits

According to the standard protocol, two to four follow-up visits every year are arranged for enrolled patients, with the same follow-up frequency formulated for regional, county, or community MMCs. The actual number of visits may be changed depending on patients' condition and compliance. The flow chart for clinical examination at each visit within one-year period are listed in Table 2. The clinical examination in the follow-up stage beyond one year are also performed with reference to Table 2.

Urinary albumin-to-creatinine ratio (UACR) will be collected every six months to define the status of proteinuria. Fundus photography and screening for diabetic neuropathy will be performed annually. The patients with moderate DR or worse will be referred to the ophthalmology department for further examination and treatment. Carotid ultrasonography, baPWV and ABI will be evaluated at least 3 times during the 5-year follow-up period (baseline, year 2 or year 3, and year 5). ECG and echocardiogram will be arranged at least twice within 5 years (baseline and year 5). The screening frequency of diabetes related complications may be adjusted if necessary.

9. Clinical Outcome Measures

9.1 Primary outcome measures: The primary outcomes include incidence of all diabetes-related clinical endpoints:

1) Mortality

- (1) Total mortality;
- (2) Cardiovascular mortality: includes fatal myocardial infarction (MI), death due

to stroke, fatal congestive heart failure, unexpected death presumed to be due to ischemic cardiovascular disease, death due to documented arrhythmia, and death due to other cardiovascular diseases;

- (3) Fatal renal failure
- 2) The Macrovascular morbidity
 - (1) Coronary heart disease
 - a) non-fatal MI or ischaemic heart disease
 - b) Coronary revascularization or coronary artery bypass surgery
 - c) Percutaneous transluminal coronary angioplasty (PTCA)
 - (2) Carotid angioplasty with or without stent; Carotid endarterectomy
 - (3) Peripheral vascular disease
 - a) Peripheral angioplasty with or without stent;
 - b) Peripheral vascular surgery (including aortic aneurysm repair);
 - c) Peripheral circulatory disorders;
 - d) Peripheral vascular disease;
 - e) Limb amputation due to vascular disease;
 - f) Gangrene.
 - (4) Stroke
 - a) Ischaemic stroke (a nonvascular etiology must be absent);
 - b) Intracerebral haemorrhage;
 - c) Subarachnoid haemorrhage;
 - d) Other and unspecified intracranial haemorrhage;
 - e) Stroke of unknown type etiology.
- 3) Non-fatal congestive heart failure
- 4) The Microvascular morbidity
 - (1) Diabetic kidney disease (DKD):
 - a) Chronic kidney disease: Estimated glomerular filtration rate (eGFR) <60 ml/min/1.73m² (as estimated by the EPI equation, eGFR=141 × min(Scr/κ, 1)^α × max(Scr/κ, 1)^{-1.209} × 0.993^{Age} × 1.018 [if female] _ 1.159

[if black], where Scr is serum creatinine in mg/dl, κ is 0.7 for females and 0.9 for males, α is -0.329 for females and -0.411 for males, min represents the minimum of Scr/ κ or 1, and max represents the maximum of Scr/ κ or 1).

- b) End-stage renal disease: Estimated glomerular filtration rate (eGFR) <15 ml/min/1.73m², or need dialysis, or need renal transplant
- c) Development of microalbuminuria (urinary albumin/creatinine ratio
 [UACR] ≥30 and < 300mg albumin per gram creatinine, or UACR ≥
 3.39 and < 33.9 mg/mmol in a random sample)
- d) Development of macroalbuminuria (urinary albumin/creatinine ratio
 [UACR] ≥ 300mg albumin per gram creatinine, or UACR ≥ 33.9
 mg/mmol in a random sample)
- (2) Diabetic retinopathy (DR):
 - a) If both eyes' images were evaluable, the more severe DR grade between the two was adopted.
 - b) If only one eye's image was gradable, the DR grading relied solely on that eye.
 - c) If no gradable image was available for either eye, the patient was classified as ungradable.
 - d) In cases of discrepancy between the on-site and qualified AI result, the more severe DR grade was selected.
 - e) Any occurrence of the following adverse events was classified as an incidence of DR: undergoing laser treatment or therapy with anti-vascular endothelial growth factor (VEGF) inhibitors, experiencing vitreous/preretinal hemorrhage, clinically significant macular edema (CSME), undergoing vitrectomy, or developing diabetes-related blindness.
- 5) Neuropathy
- 6) Cancer:

The occurrence of any of the cancers include prostate, breast, lung/bronchus, endometrial, colon, gastric, leukemia, lymphoma, pancreas, kidney/renal pelvis, rectal, and melanoma;

- Major infections: include chronic and acute infections, pulmonary and non-pulmonary;
- 8) Hospitalization for any of the above reasons.
- 9.2 Secondary Outcome Measures:
- 1) Glycated haemoglobin (HbA1c, %)
- 2) Fasting and postprandial glucose concentrations (mmol/L)
- fasting and 2-hour postprandialinsulin and C peptide levels, as well as the variables derived from these measurements (homeostasis model assessment index for assessing insulin resistance [HOMA-IR and HOMA2-IR]
- Lipids levels include triglyceride, total cholesterol, high density lipoprotein-cholesterol (HDL-c) and low density lipoprotein-cholesterol (LDL-c)
- 5) Blood pressures (mmHg)
- Body weight, and BMI: Body weight (kg) and height (m) will be combined to report BMI in kg/m²
- 7) Visceral fat (cm^2) and subcutaneous fat (cm^2)
- 8) Health related quality of life
- 9) Cognitive function
- 10) Other anthropometric parameters, include head, neck, waist, and hip circumferences
- 11) Carotid plaque and carotid intima-media thickness;
- 12) Brachial-ankle pulse wave velocity (baPWV) and ankle-brachial pressure index (ABI)
- 13) Psychological well being, using physiological parameter, questionnaire
- 14) The incremental cost per quality adjusted life year (QALY) gained. QALYs will be measured by the EuroQol-5 Dimensions (EQ-5D) questionnaire.

9.3 Safety measures:

- Hypoglycemia: any hypoglycemic episode (blood glucose concentration <70 mg/dl [3.9 mmol/l]), and severe hypoglycemic episodes requiring third party assistance;
- 2) The alterations of vital signs, 12-lead ECG,
- Laboratory abnormalities, include blood biochemistry, blood and urine routine measures;
- Adverse events (type, frequency, severity, relationship of adverse events to drug therapies).
- 9.4 Exploratory measures:

Explore the epidemiology, genetics, new biomarkers, risk factors, and prognostic methods related to diabetes and its related complications, as well as other metabolic diseases.

10. Quality assurance and quality control measures for clinical operation

[figure not shown]
The MMC's four-tiered prevention and control network infrastructure consists of the MMC leading center (MMC in Ruijin hospital, Shanghai Jiao Tong University School of Medicine, Shanghai), regional centers, county centers, and community centers (Figure 4). The MMC leading center establishes a comprehensive set of written standard operating procedures (SOPs), which are then provided to all MMCs to ensure quality assurance (QA) throughout every stage, from site construction to clinical operations. This ensures a uniform and high-quality approach to disease management across the entire network. 

Figure 4. MMC four-level prevention and control network infrastructure

During the initial stage, all staff members in each center, encompassing doctors, nurses, and technicians, will undergo comprehensive training via the MMC's specialized internet-based SOPs training platform. Engineers will also be responsible for conducting on-site training sessions to ensure proficiency in equipment operation. It is mandatory for the center staff to complete all relevant online courses and pass the subsequent examination receiving certification of qualification before commencing patient enrollment (Figure 5).

Figure 5. Certificate of qualification awarded to MMC staff after training

An independent electronic system for data acquisition, tracking, and management has been developed. This system provides real-time and automatic monitoring of data, enabling the prompt detection of any abnormal or out-of-range values. In such cases, the platform automatically sends correction reminders or queries to alert center staff. This prompts them to review data entries and make timely corrections. Additionally, to facilitate constant quality improvement across all centers, a free online support service and a WeChat working group are available to provide prompt assistance and solutions to any arising issues.

Once the baseline data entries for the initial 20 consecutive patients in each center have been completed, the quality control (QC) team from the MMC leading center will promptly conduct a remote data quality evaluation. Feedback and any queries arising from this evaluation will be promptly communicated to the respective centers for correction. Following the completion of baseline data entry for 200 consecutive patients, a second remote manual QC will be carried out to assess the operational quality and facilitate center certification. Once these steps are completed, each center will be subject to regular and ongoing data monitoring. Additionally, an automated monthly online QC report will be generated and made available online to ensure consistent operational quality across all centers.

An offline QC process has been established to guarantee precise clinical operations. First, each center is required to have a dedicated local QC staff member who will conduct a self-assessment based on the established SOPs and monthly QC reports, making necessary corrections as identified. Second, a clinical research associate from a third-party organization will conduct regular on-site monitoring. This includes checking clinical procedures, sample collection methods, verifying the consistency of source data with original medical records and online entries, as well as monitoring the follow-up process. Third, well-performing MMCs regularly hold sharing sessions to disseminate their experiences to other MMCs (Figure 6).

Furthermore, audits conducted by specialists from the MMC Quality Control Group will be conducted regularly to oversee both the standardization of facilities and workflow, as well as the operational procedures of staff members in each center. These audits ensure the maintenance of high-quality standards across all centers. 

Figure 6. MMC online and off-line training, experience sharing

To evaluate and enhance the overall quality of the centers, an annual quality ranking will be performed for all centers nationwide. This ranking will be based on various metrics, including the center's participant enrollment capacity, the quality of clinical data, the follow-up rate of participants, and their overall management abilities.

The superior centers will be awarded an honorary certificate (Figure 7). Centers that fail to pass the quality assessment for two consecutive years will be required to undergo rectification and improvement measures. Centers that fail to pass the re-assessment process after rectification will not be recertified, thus will be not allowed to be involved in subsequent scientific research analysis. This ensures that only centers meeting the highest standards of quality are certified and continue to participate in the program.

Figure 7. Certificate awarded to superior MMCs

11. Geographical disparity

All patients are respectively divided into seven regions according to the location of MMC they MMC they enrolled (Table 3).

T-LL 2	n	/ +			1	1 114	•	7	f(C1)
I able 5.	. Provin	ces/autor	nomous	region	munic	ipalit	v in	/ region	is of China
				0		1	2	. 0	

Region	Provinces				
East China	Shanghai, Jiangsu, Zhejiang, Anhui, Fujian, Jiangxi, Shangdong,				
	Taiwan				
South China Guangdong, Guangxi, Hainan, Hong kong, Macao					

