2. ONE CENTER, ONE STOP, AND ONE STANDARD MODEL IN THE MMC

All MMCs in China have the same structure in terms of facilities, layout, and databases, as well as the same routine daily operations, aiming to establish a platform with standardized diagnosis and treatment of metabolic diseases and their long-term follow-up. This platform of treatment is called the 'One Center, One Stop, and One Standard Model' (Figure 1). In the MMCs, patients can enjoy one-stop care to receive

a comprehensive series of services from registration, tests, evaluation, prescriptions, appointment follow-up, to health education. Under the guidance of the MMC Experts Committee, 492 stringent standard operational procedures (SOPs) are set up for quality control of the MMC operation (Figure 2). And we have also published MMC Guideline, Metbolic Disease Management Guideline for National Metbolic management Center which includes guidelines for diabetes diagnosis and treatment as well as the process of management in MMC [7]. Furthermore, with technological innovations, for example, the "all-in-one machine" (Figure 1), by the ingenious integration of the examination equipments, greatly shortens the process for the screening of complications. In addition, the MMC has established an independent digital medical record system integrating real-time information of patients in and outside the hospital into a centralized medical data center that can be exported through various Internet of Things (IoT) instruments, including apps, Wechat, and a teleconsultation system, to enable patient care to be extended from the MMC to anytime, anywhere outside the center (Figure 3).

MMC "All-in-One" Machine

MMC "one-center, one-stop , one-standard" layout, unified nationwide

[figure not shown]
[figure not shown]

Figure 2. Displays of MMC's SOP

NPI: National Patient Identifier; EMR, Electronic Medical Record; NLP, Natural Language Processing; SaaS, Software-as-a-Service; IoMT, Internet of Medical Thing; IMS, Intelligent management system; AI, Artificial Intelligence.

Figure 3. Internet-based electronic database management and patient care system for MMC program

3. Data collection

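### Macular edema alone makes a patient vision-threatening in 8.2.1, but it is absent from the definition of referable DR and from the 8.3 referral rule

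*Protocol*

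**What the plan says.** Section 8.2.1 (Fundus Photography) sets three retinopathy labels:

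- DR status is positive "if mild non-proliferative DR (NPDR) or above is present".
- The other two labels follow in one sentence: "referable DR (moderate NPDR or above); vision-threatening DR (VTDR, severe NPDR or above and/or clinically significant macular edema [CSME". Referable DR rests on NPDR grade alone. VTDR has two limbs joined by and/or, so either one is enough.
- The only latitude given is for one of these labels: "The definition for VTDR may be modulated and specified in certain studies". Nothing similar is said of referable DR.

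Section 8.3 (Clinical Examination at Follow-up Visits) then states who goes to the eye department: "The patients with moderate DR or worse will be referred to the ophthalmology department for further examination and treatment". CSME is not named.

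The only other place where CSME appears is section 9.1, item 4)(2)e. It lists the events that count as incident DR and includes "clinically significant macular edema (CSME), undergoing vitrectomy, or developing diabetes-related blindness".

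**The concern.** One would expect every patient labelled vision-threatening to be referable as well. As written, VTDR is not contained in referable DR, because CSME opens one category and not the other. The referral sentence in 8.3 follows the grade-only definition closely, so it can be read to leave out a condition that the protocol itself calls vision-threatening.

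What is at stake is patient referral and the consistency of two labels. No estimate, error rate or outcome depends on it. Item 4)(2)e of 9.1 already counts CSME as incident DR, and no outcome in section 9 uses referable DR or VTDR.

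**Working it through.** The protocol states no figure on this point, so there is none to reproduce. The check is to cross retinopathy grade with CSME status and apply the definitions cell by cell.

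**Inputs**

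- DR present: mild NPDR or above (8.2.1).
- Referable: moderate NPDR or above (8.2.1).
- VTDR: severe NPDR or above, or CSME, or both (8.2.1).
- Grades: none, mild, moderate, severe, above severe. This list is an assumption drawn from the wording of 8.2.1.

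| Grade | CSME | VTDR | Referable as written | Referable with CSME added |
|---|---|---|---|---|
| None | no | no | no | no |
| None | yes | yes* | **no** | yes |
| Mild | no | no | no | no |
| Mild | yes | yes | **no** | yes |
| Moderate | no | no | yes | yes |
| Moderate | yes | yes | yes | yes |
| Severe | no | yes | yes | yes |
| Severe | yes | yes | yes | yes |
| Above severe | no | yes | yes | yes |
| Above severe | yes | yes | yes | yes |

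*Only if the VTDR label can apply without NPDR. Section 8.2.1 sets DR status to positive from mild NPDR upward, so this cell depends on the reading.

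**Labels apply only to patients with DR** (4 grades × 2 = 8 cells)

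- VTDR: 4 (severe and above severe) + 2 (mild or moderate with CSME) = 6.
- Referable as written: 3 × 2 = 6.
- Both: 5. VTDR but not referable: 6 − 5 = **1 of 6**.
- After adding CSME: referable 7, both 6, gap 6 − 6 = **0 of 6**.

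**Labels apply to everyone** (5 grades × 2 = 10 cells)

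- VTDR: 4 + 3 (none, mild or moderate with CSME) = 7.
- Referable as written: 6.
- Both: 5. VTDR but not referable: 7 − 5 = **2 of 7**.
- After adding CSME: referable 8, both 7, gap 7 − 7 = **0 of 7**.

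The assumed grade list affects the denominators but not the gap. If severe and above severe are merged, VTDR occupies 6 − 2 = 4 or 7 − 2 = 5 cells, and the gap is still 1 or 2.

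**Applied to the 8.3 sentence**

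- If worse means NPDR grade, the same 1 (or 2) VTDR cells are not expressly referred.
- If VTDR counts as worse, 0 cells are left out.

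The text points both ways. The grade reading is supported because the 8.3 wording runs parallel to "referable DR (moderate NPDR or above", and because 8.2.1 uses the word worse to rank the grades of the two eyes. The wider reading is supported because 8.3 says DR and not NPDR, and because 8.2.1 introduces referable DR and VTDR together as descriptions of DR grade.

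**The case against.** The strongest reply is that no patient need be missed. Section 8.2.1 presents VTDR as a description of DR grade, and 8.3 speaks of DR, so a vision-threatening patient can be counted as worse than moderate. That reading is open. If it is adopted, only the mismatch of labels in 8.2.1 is left. The protocol does not say which reading is meant, however, and each centre would have to choose.

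Four further points deserve weight.

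- **The rule is not exclusive.** The 8.3 sentence does not restrict referral to the patients it names, and section 2 says that "492 stringent standard operational procedures (SOPs) are set up for quality control of the MMC operation". Those procedures are not shown and may contain a macular edema step. This stands as a limit on the concern, but it would not reconcile the two definitions in the protocol.
- **These patients may already be in eye care.** The document does not say how CSME is ascertained. If it is recorded from eye-clinic reports, the 8.3 edit changes little for them. The VTDR definition does sit within the fundus photography section, beside a macula-centred image of each eye. That suggests, without proving, that CSME can be found at screening.
- **Nothing requires nesting, and no outcome uses these labels.** This is correct, and it is why the point carries low severity.
- **Cells are not patients.** Also correct. The counts show that the gap exists, and they say nothing about how common it is.

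The latitude clause does not help, since it covers the VTDR definition only.

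**Conclusion.** The concern holds, at low severity. On the protocol's own definitions, mild NPDR with CSME is vision-threatening but not referable, and this case needs no interpretive assumption. CSME without NPDR joins it if the labels apply to patients without NPDR. The gap is 1 of 6 VTDR cells, or 2 of 7 on the wider frame.

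Whether the gap carries through to actual referral depends on how worse is read in 8.3, on the unseen operating procedures, and on how CSME is ascertained. The protocol gives no CSME frequency, so the number of patients affected cannot be stated.

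**What to change.** Make two wording edits:

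1. In 8.2.1, define referable DR as moderate NPDR or above and/or CSME.
2. In 8.3, refer patients with moderate NPDR or worse and/or CSME to ophthalmology.

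The second edit also removes the ambiguity by naming the NPDR scale. Section 9.1 needs no change.

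The edits call for no new data item, because the VTDR definition already needs CSME status, although how each centre obtains it is not stated. The edits make 1 cell newly referable if the labels apply only to patients with DR, and 2 if they apply to everyone. The practical cost is some additional referrals through an existing pathway, whose number cannot be derived from the document.
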